**POEM (Practice Of Embracing Each Moment) STUDY
NCT03078608**

04/19/2019

Methods

Setting

The POEM (Practice Of Embracing each Moment) study was conducted within Kaiser Permanente Northern California (KPNC), an integrated health care delivery system that provides comprehensive health care to a large, diverse community-based population of over 4.1 million individuals. KPNC provides coverage for approximately 31% of the northern California population, and its membership is similar demographically, ethnically, and socioeconomically to the area's overall population. The only exception is with regard to income; KPNC members underrepresent the very poor and the very wealthy. Participants for the POEM study were recruited from 7 KPNC oncology clinics in the San Francisco Bay Area.

Participants

We included patients with a diagnosis of cancer who were currently receiving or had received chemotherapy, targeted therapies, or immunotherapy in the prior 6 months. The inclusion criteria for both patients and caregivers included age ≥ 18 years; owning a smartphone, tablet, or computer with internet access; and understanding English. Primary informal caregivers of the patients were also eligible and invited to participate. We excluded persons who regularly meditated or prayed at least 3 times per week, were currently participating in another type of stress reduction program, were severely hearing impaired, or had severe mental illness.

Procedures

This 2-arm randomized controlled pilot trial was conducted between October 2017 and November 2018. Participants completed an online informed consent form, and study protocols and procedures were approved by the KPNC Institutional Review Board. The study was registered on ClinicalTrials.gov (NCT03078608).

Recruitment. Patients were recruited using several strategies, including clinic referrals from oncologists, oncology social workers, and nurses; brochures at each clinic; and invitation emails, followed up with phone calls. Eligible patients were identified using the KPNC electronic health record. Caregivers were recruited by patient participant referral. Patients could participate with or without caregiver participation, and caregivers could also participate without an enrolled patient. Participants who completed the study received a \$40 gift card and a year's subscription to the mindfulness program used for this trial.

Randomization. Participants were allocated to the 2 study groups using simple balanced blocked randomization, stratified by facility. Randomization was implemented by use of allocation assignment concealed in a set of sequentially numbered opaque envelopes filled by research personnel not affiliated with the trial. Caregivers who enrolled with a patient participant were assigned to the same arm as the patient.

Intervention. Participants in the intervention arm received free access to a commercially available mindfulness program, HeadspaceTM (www.headspace.com), for 8 weeks. Headspace is a self-paced program that provides guided mindfulness meditation instructions via a website or mobile application (iOS and Android). Research staff emailed participants randomized to the intervention arm device-specific instructions for downloading the Headspace app and information about the program. Research staff checked in with participants over the phone a few days after emailing the instructions and provided support for setting up Headspace over the phone, if needed.

Participants were asked to complete Headspace sessions on a daily basis during the 8-week intervention. They were encouraged to first complete the 30-day Foundation Course, which teaches users the basics of mindfulness meditation, then the cancer pack, which was designed specifically for individuals affected by cancer. They also had the option to choose other 10- to 30-day courses that are more condition- or situation-specific, such as "Anxiety," "Stress," "Acceptance," "Relationships," or "Sleep," or single meditation sessions. All Headspace courses teach mindfulness using various basic techniques, including breathing exercises, body scan (to mindfully pay attention to different parts of one's body—one of the most basic exercises in the MBSR program), noting (being aware of any emotions that may be arising at the moment), and visualization (visualizing images such as sun shining on the entire body). The length of the sessions can be set from 10 to 20 minutes. The length was initially set to 10 minutes for all participants. In addition to the daily, progressive audio instruction, there are short (1-2 minutes) lecture videos every several days designed to increase the understanding of mindfulness and to encourage its integration into daily life. Headspace can be set up to send reminders using push notifications, and study staff made phone calls if an intervention participant completed fewer than 3 Headspace sessions in a week.

Wait-list Control Arm. Participants randomized to the waitlist control arm received usual care and were asked not to start any stress reduction programs during the study period. On completion of the 8-week survey, the control participants were provided with a year's subscription to Headspace and instructions on downloading the app.

Outcome Measures

Retention. The retention rate was measured as the proportion of enrolled participants who completed the 8-week survey (the primary outcome time point).

Adherence. The Headspace program automatically collects adherence data, including date, time, length, and name of each session to which participants listened, identified by a study ID. Headspace transferred these adherence data to the researchers monthly during the study. Using these data, we calculated the proportion of days during the 8-week intervention period that each participant used the program for any amount of time.

Participant-Reported Measures. We collected outcome data using self-administered online surveys using DatStat software (DatStat Ilume, version 6.1.18.19, Seattle, WA) at the time of consent (baseline survey) and immediately post-intervention (8-week survey) using validated questionnaires as follows.

Distress. The NCCN Distress Thermometer was used to assess current distress level. Respondents were asked to rate their level of distress during the past week by choosing a number, with 0 indicating no distress and 10 extreme distress.

Anxiety and depression. We used the 14-item Hospital Anxiety and Depression Scale (HADS) to assess anxiety and depression. Higher scores indicate greater anxiety and depression.

Pain. The PROMIS Pain Intensity numeric rating scale asks participants to rate average pain level in the past 7 days on a scale of 0 (“no pain”) to 10 (“worst imaginable pain”). The 8-item PROMIS Pain Interference scale assesses extent to which pain interfered with functional activities during the past 7 days. Higher scores indicate more interference due to pain.

Sleep quality. The 8-item PROMIS Sleep Disturbance scale assesses sleep disturbance during the past 7 days. A higher summary score indicates worse sleep disturbance.

Quality of life. We used the 27-item Functional Assessment of Cancer Therapy General Scale (FACT-G) to assess QoL in patients. FACT-G asks respondents to rate their QoL in 4 domains (physical, social/family, emotional, and functional well-being). Caregiver QoL was determined using the Caregiver Quality of Life Index–Cancer (CQOLC) scale. The CQOLC gauges the daily and overall impact caregiving has on respondents’ QoL. Higher scores indicate better QoL on both scales.

Fatigue. The 9-item Brief Fatigue Inventory assesses the severity and impact of fatigue on various aspects of life in the past 24 hours. Higher scores indicate greater fatigue.

Posttraumatic growth. The 21-item Posttraumatic Growth Inventory (PTGI) assesses 5 factors of posttraumatic growth, positive change experienced because of a traumatic event or crisis—relating to others, new possibilities, personal strength, spiritual change, and appreciation of life. Respondents are asked to rate to what extent they have seen the listed changes as a result as a crisis in their lives. We modified the wording to ask about changes as a result of their (patients) or their loved one’s (caregivers) cancer diagnosis. Higher scores indicate greater post-traumatic growth.

Mindfulness. The 24-item Five Facet Mindfulness Questionnaire–Short Form (FFMQ-SF) measures 5 factors representing elements of mindfulness: observing, describing, acting with awareness, nonjudging of inner experience, and nonreactivity to inner experience. Higher scores indicate greater mindfulness.

Post-Intervention Interview. We conducted phone interviews with participants after they completed the 8-week intervention period to obtain qualitative feedback regarding the study. Question topics included benefits of using Headspace, things they liked about Headspace or thought could be improved, suggestions for improving the experience of study participants, and experience being in the wait-list control arm.

Data Analyses

Data from patient participants and caregiver participants were analyzed separately. We described baseline distributions between arms. Retention rates were calculated by dividing the number of participants who completed the 8-week surveys by the number of randomized participants. We used the program usage data collected by Headspace to calculate intervention adherence rates—the percent of days within the 8-week intervention period that participants engaged in at least one Headspace session of any length.

To obtain preliminary efficacy results, we performed repeated measures analysis of variance tests comparing change in outcome measures between baseline and 8-week follow-up survey between intervention and control arms using all participants who completed both surveys. Cohen’s d effect size was calculated by taking the difference between group mean change scores and dividing by the pooled standard deviation. All analyses were intent-to-treat. As a pilot study, this randomized clinical trial was not adequately powered to detect statistically significant differences between groups. As such, standardized effect sizes were calculated to demonstrate effects and trends. Effect sizes of approximately 0.2, 0.5,

and 0.8 are generally considered small, medium, and large effects, respectively.

As a supplementary analysis, we conducted dose-response per-protocol analyses, repeating the analysis but stratifying intervention participants by level of adherence to the mindfulness intervention protocol (percent of days during intervention period used Headspace: <50% and $\geq 50\%$) and comparing with the control participants.

Interviews were transcribed and uploaded into Nvivo 12 software. Inductive thematic analysis was employed to identify and develop codes on themes related to mindfulness benefits, the interface experience, the cancer patients'/caregivers, perspective of mindfulness. One primary coder (MM) initially coded each interview and met with a secondary coder (AA) to discuss the coding, identify disagreements, and ensure accuracy of codes. This article focuses on the feasibility component of the qualitative interviews.

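### The patient analysis compares raw change between arms, adjusting neither for the baseline score nor, in a sensitivity model, for treatment phase; the cost is some precision, not bias.

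*Combined protocol and SAP*

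**What the plan says.** Under Methods, Participants, patients are eligible if they "were currently receiving or had received chemotherapy, targeted therapies, or immunotherapy in the prior 6 months". Either condition is enough, so two treatment phases enter the same patient group. Under Recruitment, "Eligible patients were identified using the KPNC electronic health record".

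Under Randomization, allocation used "simple balanced blocked randomization, stratified by facility". Patients were "recruited from 7 KPNC oncology clinics in the San Francisco Bay Area", so there are seven strata, and treatment phase is not a stratification factor.

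Under Data Analyses, patients and caregivers are analysed separately, but patients are not divided by treatment phase. The efficacy method is stated as "we performed repeated measures analysis of variance tests comparing change in outcome measures between baseline and 8-week follow-up survey", "using all participants who completed both surveys". No covariate is named. Cohen's d is the difference in mean change divided by a pooled standard deviation, and no confidence interval is mentioned. Baseline distributions are described by arm, but the variables are not listed. The section says that the pilot is not adequately powered, that effect sizes serve to show effects and trends, and that about 0.2 counts as small.

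**The concern.** With two time points, the arm-by-time test in a repeated measures ANOVA is the same as an unadjusted comparison of change scores. The baseline score enters only by subtraction, with a fixed coefficient of one, and no other baseline information is used.

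Two things are left unused. The first is the baseline score as a covariate, which is available for every outcome because the baseline survey is completed at consent. The second is treatment phase. Two patients with the same baseline fatigue score, one in treatment and one recovering from it, may be expected to change differently over 8 weeks. The baseline score alone would not capture that.

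The point matters mainly because the plan relies on the size of d rather than on a test. If one arm happened to hold more recovering patients, a raw d reported without an interval would include that difference, and a reader could not see it.

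**Working it through.** **No figure to reproduce.** The documents state no sample size, SD, on-treatment share, or difference in change between phases. The calculation below is illustrative.

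**Inputs from the documents.** Two arms in balanced allocation, read as 1:1 (Randomization); seven clinics (Setting); raw change and unadjusted d, with a small effect at 0.2 (Data Analyses).

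**Assumptions.** n = 15, 30 or 45 patients per arm; share on treatment p = 0.5; difference in mean change between phases g = 0.3, 0.5 or 0.8, in units of the SD of change; facility blocking does nothing to balance phase.

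**Step 1: chance imbalance.** The between-arm difference in the share on treatment has SD √(2p(1−p)/n).
- n = 15: √(0.5/15) = 0.183
- n = 30: √(0.5/30) = 0.129
- n = 45: √(0.5/45) = 0.105

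**Step 2: shift in d, 95% range.** 1.96 × g × SD.

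| n per arm | g = 0.3 | g = 0.5 | g = 0.8 |
|---|---|---|---|
| 15 | ±0.11 | ±0.18 | ±0.29 |
| 30 | ±0.08 | ±0.13 | ±0.20 |
| 45 | ±0.06 | ±0.10 | ±0.17 |

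**Step 3: how often imbalance alone matters.** The shift is taken as normal with mean 0 and SD g × SD(imbalance).
- n = 30, g = 0.5: the SD is 0.5 × 0.129 = 0.065. The shift reaches 0.2 in either direction with probability 0.2%, and 0.1 with probability 12%.
- n = 30, g = 0.8: the SD is 0.103, and the probabilities are 5.3% and 33%.
- n = 15, g = 0.5: the SD is 0.5 × 0.183 = 0.091, so 0.2 is 2.19 SDs out, with probability 2.8%.

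**Step 4: share of the total uncertainty.** The variance of d is about 2/n. The part due to phase is g² × 2p(1−p)/n, so its share is R² = g²p(1−p): 2% (g = 0.3), 6% (g = 0.5) or 16% (g = 0.8). Removing it multiplies the standard error by √(1−R²). At n = 30 the standard error is √(2/30) = 0.258. It becomes 0.250 at g = 0.5 (a 3.2% cut) or 0.237 at g = 0.8 (an 8.3% cut).

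**Step 5: is it bias?** In 40,000 simulated trials with no true effect, in each of four settings (n = 30 or 50, g = 0.5 or 0.8), the unadjusted test rejected in 4.8% to 5.0% and mean d was 0 to within 0.001. At n = 30, |d| reached 0.2 in about 44% of null trials. After adjustment the figure is about 42% (g = 0.5) or 40% (g = 0.8).

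**Step 6: the baseline score.** Let ρ be the correlation between baseline and 8-week scores, with equal variance σ² at both times. A change score has variance 2σ²(1−ρ). The 8-week score given baseline has variance σ²(1−ρ²). The ratio of the second to the first is (1+ρ)/2, which is below 1 for any ρ below 1. Baseline adjustment therefore gains precision over the planned comparison, apart from the one degree of freedom it uses. The documents give no ρ, so the gain cannot be sized.

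**The case against.** A reader might infer that treatment phase is a strong driver of 8-week change and that pooling the phases can by itself mimic or hide a small effect. The documents do not support this. Nothing in them relates phase to change, and the direction is also assumed. At 30 per arm and a 0.5 SD gap, imbalance alone amounts to a full 0.2 in about 1 trial in 500. The widest value in the table, ±0.29, pairs the smallest assumed sample with the largest assumed gap.

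A reader might also infer bias. Randomisation prevents that: chance imbalance averages out, the test keeps its error rate, and the variation is already within the standard error. The same could be said of any prognostic variable left out of the model. Mixed eligibility is not an error in a feasibility pilot, and the plan openly says that power is inadequate and the efficacy results preliminary.

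Three practical objections also stand:
- Current versus past treatment is not stated to have been recorded as a study variable. That it is available is an inference from the eligibility rule and the use of the health record.
- A yes/no term is crude. It treats a patient one week past therapy like one five months past.
- The trial ran from October 2017 to November 2018 and the document, dated April 2019, is in the past tense, so a treatment term added now is post hoc.

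The plan may already tabulate treatment status, since its baseline variables are not listed; omission cannot be asserted. None of this answers the narrower point that d is computed without baseline-score adjustment and without a stated interval.

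**Conclusion.** The point holds as a modest improvement in precision and reporting. The plan pools two treatment phases, stratifies by facility only, and derives d from unadjusted mean changes when the baseline score is available. Under the assumptions of 15 to 45 patients per arm, half on treatment, and a 0.5 SD gap, chance imbalance in phase moves d within about ±0.18 to ±0.10, usually only part of a small effect. Adjusting for phase would cut the standard error by about 3%. The general case rests on baseline-score adjustment and an interval around d; the treatment term is a check on robustness. Sample size remains the dominant limit whichever model is used.

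One route to imbalance lies outside these figures. The analysis uses completers of both surveys, and randomisation does not protect against dropout that differs by phase and arm. The documents do not show that this happened.

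**What to change.** For each patient outcome, model the 8-week score on arm and baseline score. Compute the standardised effect, with a confidence interval, from the adjusted arm difference, and state which SD is the divisor. Show the planned change-score result beside it, since the analysis is described as already performed.

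Add a sensitivity model that also includes on-treatment status at baseline (yes/no, from the health record), with facility included if the sample allows. Label the treatment term post hoc.

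Show treatment status by arm for randomised patients and, separately, for completers of both surveys.

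Cost: two degrees of freedom for baseline score and treatment status, and up to six more for seven facilities. At 15 per arm, residual degrees of freedom fall from 28 to 26, or to 20 with facility, which is why facility is conditional. No new survey is needed, though treatment status may have to be extracted from the record. The gain from the treatment term is likely to be small.

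### Allocation was stratified by facility across 7 clinics, but the efficacy model has no facility term; patient tests may be mildly conservative and caregiver balance by facility is not secured

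*Combined protocol and SAP*

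**What the plan says.** **Design.** Under Setting: "Participants for the POEM study were recruited from 7 KPNC oncology clinics in the San Francisco Bay Area". Under Procedures, Randomization: "Participants were allocated to the 2 study groups using simple balanced blocked randomization, stratified by facility". The same paragraph adds: "Caregivers who enrolled with a patient participant were assigned to the same arm as the patient". The Recruitment paragraph lets patients join with or without a caregiver, and lets caregivers join without an enrolled patient.

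**Analysis.** Under Data Analyses: "Data from patient participants and caregiver participants were analyzed separately". For efficacy, "we performed repeated measures analysis of variance tests comparing change in outcome measures between baseline and 8-week follow-up survey between intervention and control arms", restricted to people who completed both surveys. For Cohen's d, the "effect size was calculated by taking the difference between group mean change scores and dividing by the pooled standard deviation". No facility term, stratified test or other covariate is named for the efficacy analysis.

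**Purpose.** The section also says: "As a pilot study, this randomized clinical trial was not adequately powered to detect statistically significant differences between groups". Effect sizes are offered instead, to show effects and trends. The document gives no sample size, alpha, block size or SD.

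**The concern.** Blocking within facility makes the arms nearly equal in size at each clinic, so facility differences in mean change largely drop out of the arm comparison. An analysis without facility does not use this. It leaves the between-facility variance in the error term and reports a standard error for a design less balanced than the one that was run. The usual rule is to analyse as randomised.

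The caregiver analysis raises a separate issue. Co-enrolled caregivers take no envelope of their own. They are whichever part of the patient blocks brought a caregiver, and a part of a balanced block need not be balanced. Because caregivers are analysed on their own, the patients' balance does not carry over in full.

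At stake is some precision in a study that is already short of it, and some avoidable noise in the caregiver effect sizes.

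**Working it through.** The plan states no figure to reproduce, so the check sets bounds under assumed inputs.

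**From the document:** 7 facilities; balanced blocks within facility (read as 1:1); two time points; test of change by arm; d on the pooled SD.

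**Assumed:** block size 4; N = 30, 60 or 100 analysed; facility share of the variance of change (ρ) from 0 to 0.20; true d of 0 or 0.5; two-sided alpha 0.05; 4,000 simulated trials per setting.

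**1. Upper bound for patients.** With exact balance in every facility, the unadjusted standard error is too large by at most 1/√(1−ρ):

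- ρ = 0.05: 1/√0.95 = 1.026
- ρ = 0.10: 1/√0.90 = 1.054
- ρ = 0.20: 1/√0.80 = 1.118

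Unfinished blocks bring the real figure below this.

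**2. Simulation for patients.** The ratio is the mean standard error from the unadjusted model over the actual SD of the estimate. Rejection rates compare the model without and with facility as a fixed effect.

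| N | ρ | Ratio, d = 0 runs | Ratio, d = 0.5 runs | Type I error, without / with | Power at d = 0.5, without / with |
|---|---|---|---|---|---|
| 60 | 0.05 | 0.257/0.251 = 1.02 | 0.256/0.254 = 1.01 | 4.3% / 5.0% | 47.8% / 48.4% |
| 60 | 0.10 | 0.254/0.251 = 1.01 | 0.255/0.245 = 1.04 | 4.4% / 5.6% | 48.8% / 51.8% |
| 60 | 0.20 | 0.253/0.236 = 1.07 | 0.254/0.227 = 1.12 | 3.5% / 5.2% | 47.9% / 55.6% |
| 100 | 0.05 | 0.199/0.197 = 1.01 | 0.199/0.197 = 1.01 | 5.0% / 5.5% | 69.8% / 70.9% |
| 100 | 0.10 | 0.198/0.190 = 1.04 | 0.198/0.188 = 1.05 | 3.7% / 4.5% | 72.3% / 75.0% |
| 100 | 0.20 | 0.197/0.178 = 1.11 | 0.196/0.181 = 1.08 | 2.9% / 4.8% | 72.3% / 79.0% |

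Monte Carlo error is about 0.3-0.4 points on type I error and 0.8 points on power. An SD from 4,000 runs carries a relative error of 1/√8000 = 1.1%, which is why paired ratios differ.

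**3. Bias for patients.** The mean difference averages 0.489-0.508 for a true 0.5, and agrees within 0.003 with and without facility. Standardising by the within-facility SD would only rescale d, by the factors in step 1: 0.50 becomes 0.513, 0.527 or 0.559.

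**4. Very small samples.** At N = 30 and ρ = 0, a fixed facility term raises the standard error from 0.362 to 0.372 and lowers power from 27.1% to 25.2%. Going from 28 to 22 degrees of freedom raises the critical t by 1.2%.

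**5. Caregivers.** Assume that 30% or 50% of patients bring a caregiver. The table gives the SD of the shift in the arm difference caused by facility imbalance alone, in SD units. The last column divides the caregiver figure by the ordinary standard error, 2/√n, at the expected number n of caregivers.

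| Patients, share | ρ | Patients | Caregivers | Caregiver shift above 0.10 | Relative to ordinary SE |
|---|---|---|---|---|---|
| 60, 30% (n = 18) | 0.05 | 0.017 | 0.088 | 22% | 0.088/0.471 = 0.19 |
| 60, 30% (n = 18) | 0.10 | 0.024 | 0.126 | 39% | 0.126/0.471 = 0.27 |
| 60, 50% (n = 30) | 0.05 | 0.017 | 0.059 | 9% | 0.059/0.365 = 0.16 |
| 100, 30% (n = 30) | 0.05 | 0.010 | 0.068 | 14% | 0.068/0.365 = 0.19 |
| 100, 50% (n = 50) | 0.05 | 0.010 | 0.045 | 3.5% | 0.045/0.283 = 0.16 |

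Caregivers lose most of the balance that patients have, but the resulting shift is a modest part of the sampling error that the unadjusted standard error already includes.

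**6. Which facility term acts.** With two time points, the arm-by-time test is a test on within-person differences, so anything constant over time cancels. In a simulated dataset with facility differences in change, adding a facility main effect left the arm-by-time estimate and standard error at 0.737 and 0.198. Only facility-by-time, or facility in a change-score model, alters that test.

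**The case against.** The case for leaving the plan alone is fair in several respects:

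- **Purpose.** This is a declared underpowered pilot with descriptive effect sizes. Retention and adherence are unaffected.
- **Outcome.** It is within-person change, so stable facility differences in level have already cancelled. Only differences in mean change matter, and the document gives no sign of their size.
- **Recruitment.** It was not purely clinic-driven. Eligible patients were found through the health record and invited by email and phone, and no reason is given for stratifying by facility.
- **Caregivers.** Co-enrolled caregivers inherit an arm that was blocked in the patient's facility, so some balance survives. Those joining without a patient fall outside the same-arm rule.

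All of this stands, and it limits the size of the point. It does not remove the mismatch between design and analysis.

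Stronger readings are tempting, and the document does not support them. A reader might infer that the patient effect sizes are distorted. They are not: balance within facility keeps the mean difference unbiased, and d on the total SD is a legitimate standardisation. A reader might fear false positives, but the error runs the other way. A reader might think confidence intervals or error bars are wrong, but none are described. A reader might call the caregiver comparison biased, but the imbalance is random and the ordinary standard error covers it.

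**Conclusion.** The mismatch is real and its consequences are small. For patients, omitting facility costs precision only. The loss is negligible if facility explains 5% or less of the variance in change. It is more visible at 10-20%, where power at d = 0.5 rises with adjustment by 3 to 8 points at N = 60 (51.8 − 48.8 = 3.0; 55.6 − 47.9 = 7.7). Using only people who completed both surveys could loosen the block balance somewhat.

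For caregivers, balance by facility is not guaranteed. A chance shift of 0.10 in d, half of the 0.2 that the document calls small, is plausible under some assumed settings. A facility term would remove part of that noise.

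The mismatch rests on the text. Every size given here rests on assumed sample sizes, block size, caregiver share and facility variance. Nothing in the document shows that a conclusion would change.

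**What to change.** For each outcome, fit the change score with arm and facility. Adding facility-by-time to the repeated measures model is equivalent; a facility main effect or a facility random intercept in that two-time-point model is not enough. Report the facility-adjusted difference in mean change with its standard error. Keep d standardised by the total pooled SD, as now planned, so that it stays comparable with other studies.

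For caregivers, use a random facility intercept in the change-score model, or pool the smallest facilities, so that sparse cells do not break the fit.

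No new data should be needed, since facility was required to randomise. The cost is up to 7 − 1 = 6 degrees of freedom, fewer with a random intercept or pooling. In a very small sample where facility explains little, this may slightly reduce precision. Showing the unadjusted result alongside lets the reader see the difference.

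### Could staff phone low users on a weekly rule when usage data reached the researchers only monthly?

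*Combined protocol and SAP*

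**What the plan says.** The Intervention paragraphs under Procedures ask for daily use over 8 weeks: "Participants were asked to complete Headspace sessions on a daily basis during the 8-week intervention". They describe three kinds of support:

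- A set-up contact: "Research staff checked in with participants over the phone a few days after emailing the instructions", with help over the phone if needed.
- Optional push reminders from the app.
- A low-use rule: "study staff made phone calls if an intervention participant completed fewer than 3 Headspace sessions in a week".

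The Adherence paragraph under Outcome Measures describes the usage data: "The Headspace program automatically collects adherence data, including date, time, length, and name of each session to which participants listened". It continues: "Headspace transferred these adherence data to the researchers monthly during the study". The use given for the data follows directly: "Using these data, we calculated the proportion of days during the 8-week intervention period that each participant used the program for any amount of time".

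Data Analyses repeats the adherence definition and adds a supplementary analysis "stratifying intervention participants by level of adherence to the mindfulness intervention protocol", with the cut at 50% of days. The same section says that "this randomized clinical trial was not adequately powered to detect statistically significant differences between groups".

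**The concern.** The call rule needs a count for each participant each week. The only route described for usage data delivers it about once a month. Surveys were taken only at baseline and 8 weeks, and the document mentions no dashboard, interim report or self-report of sessions. Read together, the two statements suggest that staff often learned of a low week well after it had passed, and sometimes after the intervention was over.

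Adherence is one of the two feasibility outcomes listed first, and the calls are the only continuing staff contact described after set-up. If calls were late or sparse, the adherence rate was obtained with less support than a reader would suppose, and a later trial that phoned weekly would be delivering something different. The calls also act on the variable that defines the supplementary strata. Fewer than 3 sessions means use on at most 2 of 7 days (2/7 = 29%), below the 50% cut.

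**Working it through.** The plan gives no figure on this point to reproduce. The check is one of timing, followed by a check of what depends on the timing.

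**Inputs from the document.** The intervention lasts 8 weeks, or 56 days (Intervention). The trigger is a weekly count (Intervention). Transfer is monthly (Adherence).

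**Assumptions.** Transfers come every T days, with T from 28 to 31 and 30.4 as the central value. Start dates fall uniformly within the transfer cycle. There is no processing delay. The monthly file is the only source; the document does not say this, and it is the assumption least favourable to the plan.

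**Lag.** The mean wait from the end of a week to the next transfer is T/2: 28/2 = 14.0 days, 30.4/2 = 15.2 days, 31/2 = 15.5 days. The longest wait is T.

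**Seen within a week.** The share is 7/T: 7/28 = 25%, 7/30.4 = 23%, 7/31 = 23%.

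**Seen before the intervention ends.** Week k ends on day 7k, so the probability is min(1, (56 − 7k)/T). With T = 30.4:

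| Week | Days left | Probability |
|---|---|---|
| 1, 2, 3 | 49, 42, 35 | 1.00 each |
| 4 | 28 | 0.92 |
| 5 | 21 | 0.69 |
| 6 | 14 | 0.46 |
| 7 | 7 | 0.23 |
| 8 | 0 | 0.00 |

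The sum is 5.30. Over 8 weeks that is 5.30/8 = 66% seen in time and 34% seen late.

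**Week 8.** It ends on day 56, so no feed, weekly or daily, can show its complete count before the intervention is over. Charging it to the monthly schedule overstates the problem. Over weeks 1 to 7, 5.30/7 = 76% are seen in time and 24% late. With T = 28 the sum is 5.50, and (7 − 5.50)/7 = 21% are late. With T = 31 it is 5.26, and (7 − 5.26)/7 = 25% are late.

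**Transfers per participant.** At least one always falls before day 56. Two do so for 81% of start dates at T = 31, 84% at T = 30.4 and 100% at T = 28.

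**What depends on the timing.**

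- Adherence rate: days with any session divided by 56. Each session carries its own date, so the arrival date of the file does not enter.
- Supplementary strata: the cut is 0.5 × 56 = 28 days of use, from the same dated log.
- Between-arm comparisons: these use survey scores at baseline and 8 weeks by randomised arm. Neither calls nor usage files enter.

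**The case for a change.** The strongest case for the concern is that the text is deficient either way. If staff had a weekly source, it is not recorded; if they had none, the call rule is described as prompter than it was. On monthly data alone about three quarters of low weeks would be noticed more than 7 days late, and this barely moves between 28 and 31 days. In a feasibility pilot, the support behind the adherence figure is part of what a successor trial needs to know.

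The reporting point stands: the document does not say how or how often staff learned the weekly counts.

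The stronger claim, that the two statements cannot both be true, does not stand. The monthly transfer appears as an outcome data source with one stated use, calculating the proportion of days. The calls are described elsewhere, as made, with no link to that file. Silence about a weekly view is not evidence that none existed. The rule also sets no deadline for a call, so one made late after a low week still fits the sentence. Nor does the document credit the adherence rate to the calls, so no stated conclusion depends on how promptly they were made.

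**Conclusion.** No change to the plan follows. What is left is a missing operational detail: the source that triggered the calls. The study team can supply it from its own records when reporting the intervention.

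On the least favourable reading, low weeks come to light 14.0 to 15.5 days after they end on average, and 21% to 25% of shortfalls in weeks 1 to 7 are seen too late for a call during the intervention. Those figures rest on a 28 to 31 day cycle, uniform start dates, no processing delay and no other source. They describe delayed support, which bears on how the adherence rate is read but not on how it is calculated. No rate, stratum or between-arm estimate would differ.

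The trial ran from October 2017 to November 2018 and the document is dated 04/19/2019. A more frequent feed or a prospective call log could not alter how this intervention was delivered.
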